**LIST OF ABBREVIATIONS**

Abbreviation	Definition
ADM	Admission
Ae	Urinary excreted amount of test compound
Ae%	Urinary excreted amount of test compound expressed as a percentage of the dose administered
AE	Adverse event
ALT	Alanine aminotransferase
AST	Aspartate aminotransferase
AUC	Area under the plasma concentration-time curve
AUC 0-∞	Area under the plasma concentration-time curve from time zero to infinity
AUC 0-24h	Area under the plasma concentration-time curve from time zero to 24 hours
AUC 0-last	Area under the plasma concentration-time curve from time zero to the last measurable concentration
AUC 0-t	Area under the plasma concentration-time curve over the dosing interval
BED	Binge eating disorder
BMI	Body mass index
cAMP	Cyclic adenosine monophosphate
cGMP	Cyclic guanosine monophosphate
CI	Confidence interval
CL/F	Apparent oral clearance
CLR	Renal clearance
C max	Maximum plasma concentration
CS	Clinically significant
CSR	Clinical Study Report
CYP	Cytochrome P450
DSM-V	Diagnostic and Statistical Manual of Mental Disorders
ECG	Electrocardiogram
eCRF	Electronic case report form
EMA	European Medicines Agency
	
FDA	Food & Drug Administration
FSH	Follicle stimulating hormone
FU	Follow-up Visit
GCP	Good Clinical Practice
GLP	Good Laboratory Practice
hERG	Human ether-a-go-go-related gene
HIV	Human immunodeficiency virus
HPF	Highly palatable food
ICF	Informed Consent Form
ICH	International Council for Harmonisation
IEC	Independent Ethics Committee
IMP	Investigational Medicinal Product
Kel	Terminal elimination rate constant
K p brain	Brain to plasma concentration ratio
LD D	Last day of dosing
LF	Linearity factor
LS	Least square
MAD	Multiple ascending dose
MedDRA	Medical Dictionary for Regulatory Activities
MHRA	Medicines and Healthcare products Regulatory Agency
MRT	Mean residence time

Europe/Mitsubishi Tanabe Pharma Europe Ltd  
STUDY PROTOCOL

Abbreviation	Definition
MTDA	Mitsubishi Tanabe Pharma Development America
MTPC	Mitsubishi Tanabe Pharma Corporation
MTPE	Mitsubishi Tanabe Pharma Europe Ltd
n	Number of subjects
N	Number of observations
NCS	Not clinically significant
NOAEL	No observed adverse effect level
NR+NS	Non-restricted feeding and not exposed to stress
PDE	Phosphodiesterase
PK	Pharmacokinetic(s)
QA	Quality Assurance
QP	Qualified Person (pharmacist responsible for IMP release at the site)
QTcF	Corrected QT interval using Fridericia's formula
R+S	Restricted feeding and exposed to stress
RA	Ratio of accumulation
SAD	Single ascending dose
SAE	Serious adverse event
SAP	Statistical Analysis Plan
SCR	Screening Visit
SD	Standard deviation
SOC	System Organ Class
SOP	Standard Operating Procedure
SUSAR	Suspected unexpected serious adverse reaction
$t_{1/2}$	Plasma terminal elimination half-life
TEAE	Treatment-emergent adverse event
$t_{max}$	Time to maximum plasma concentration
TMF	Trial Master File
UK	United Kingdom
ULN	Upper limit of normal
USA	United States of America
VAS	Visual analogue scale
$V_{ss/F}$	Apparent volume of distribution at steady state
WMA	World Medical Association

## Europe/Mitsubishi Tanabe Pharma Europe Ltd

## STUDY PROTOCOL

## PROTOCOL SYNOPSIS

Protocol number:	MT-6345-E01
Protocol title:	A Randomised, Double-Blind, Placebo-Controlled Phase I Study to Investigate the Safety, Tolerability and Pharmacokinetics of Single and Multiple Ascending Doses of MT-6345 in Healthy Subjects; Including Investigation of the Effect of Food, Gender and Race on the Pharmacokinetics of a Single Dose of MT-6345 in Healthy Subjects
Sponsor:	Mitsubishi Tanabe Pharma Development America Inc. [REDACTED]
EU Representative:	Mitsubishi Tanabe Pharma Europe Ltd [REDACTED]
Principal Investigator:	[REDACTED]
Development phase:	Phase I
Investigational Medicinal Product (IMP):	MT-6345 [REDACTED] and [REDACTED] capsules. Placebo capsule to match all active MT-6345 capsule strengths.
Reference product:	Not applicable.
Treatment duration:	Subjects in Part 1 (single ascending dose [SAD]), Part 4 (gender effect) and Part 5 (race effect) will participate in one single dose treatment period. A single cohort from Part 1 (anticipated to be Cohort 3; [REDACTED] MT-6345) will be selected to return for a second treatment period to investigate the effect of food on MT-6345 (Part 2). There will be a minimum of 15 days between the last dose administration in Part 1 and the first dose administration in Part 2. Subjects in Part 3 (multiple ascending dose [MAD]) will participate in one treatment period and receive a once daily dose of MT-6345 for at least 14 days. The duration of dosing in Part 3 may be altered based on review of emerging data from Part 1, but will not exceed 28 days.
Objectives:	
Primary Objective To evaluate the safety and tolerability of single and multiple ascending oral doses of MT-6345 administered to healthy subjects.
 
Secondary Objectives
 
 
• To investigate the pharmacokinetic (PK) profile of MT-6345 following single and multiple ascending oral doses administered to healthy male subjects.
 
• To investigate the effect of food and race on the PK profile of MT-6345 following a single oral dose administered to healthy subjects.
 
• To investigate the effect of gender on the PK profile of MT-6345 following a single oral dose administered to healthy female subjects.
 

## Europe/Mitsubishi Tanabe Pharma Europe Ltd

## STUDY PROTOCOL

	
 
• To investigate the effect of MT-6345 drug concentration on QT prolongation and QTc interval following single and multiple oral doses administered to healthy subjects.
 
 
[REDACTED]

Study design:	
This is a Phase I, randomised, double-blind, placebo-controlled, single-centre study, comprising five parts. It is planned to randomise 100 subjects in this study. One additional cohort of 8 subjects and one cohort of 12 subjects may be added to Parts 1 and 3, respectively. Therefore, up to 120 subjects may be included in the study.
 
Part 1: Single ascending dose (SAD)  Up to 48 healthy Caucasian males, aged 18 to 55 years who meet the study criteria will be allocated to six cohorts of 8 subjects each. One additional cohort of 8 male subjects may be enrolled (e.g., in case the mean maximum observed human exposure value at the highest dose is at least 50% lower [i.e., 22,625 ng.h/mL] than the area under the plasma concentration-time curve [AUC] at the no observed adverse effect level [NOAEL] in rat [45,250 ng.h/mL]). In each cohort, 6 subjects will be randomised to receive a single dose of MT-6345 and 2 subjects will be randomised to receive a matching dose of placebo.  All cohorts will have 2 sentinel subjects of whom 1 subject will receive MT-6345 and 1 subject will receive matched placebo. The remaining 6 subjects, of whom 5 subjects will receive MT-6345 and 1 subject will receive placebo, will be dosed at least 24 hours following the sentinel subjects.  The dose levels are planned to be administered in ascending order. Subjects will receive a single dose of MT-6345 or placebo in a fasted state (for at least 10 hours). Progression to the next dose level, and dose selection, will be based on all available safety and tolerability data up to at least 48 hours post-dose and available PK data (up to at least 24 hours post-dose) from a minimum of 6 subjects (MT-6345 n≥4) in the preceding dose cohort.  The dose administered to Cohort 1 will be [REDACTED]. The dose escalation factor applied after each cohort will not exceed five-fold for Cohorts 1 to 2, four-fold for Cohorts 2 to 3 and will not exceed three-fold thereafter. The anticipated dosing schedule is [REDACTED], [REDACTED], [REDACTED], [REDACTED] and [REDACTED]. The maximum dose in Part 1 (SAD) is anticipated to be [REDACTED] however, this will be selected based upon emerging PK, safety and tolerability data from previous cohorts.
 
Part 2: Food effect  A single cohort from Part 1 (anticipated to be Cohort 3; [REDACTED] MT-6345) will be selected to return for a second treatment period to investigate the effect of food (after a Food & Drug Administration [FDA]-approved high-fat breakfast) on the PK of MT-6345. There will be a minimum of 15 days between the last dose administration in Part 1 and first dose administration in Part 2. Subjects in Part 2 will receive the same dose (active or placebo) that they received in Part 1.


Europe/Mitsubishi Tanabe Pharma Europe Ltd

STUDY PROTOCOL

	
The dose and cohort selected for Part 2 will not be confirmed until safety, tolerability and PK data from the intended dose level in Part 1 has been reviewed and deemed acceptable. The intention is for all eight subjects to be dosed sequentially on the same day.
 
Part 3: Multiple ascending dose (MAD)
 
A total of 36 healthy Caucasian males, aged 18 to 55 years, who meet the study eligibility criteria, will be allocated to three cohorts of 12 subjects each. An additional cohort of 12 healthy male subjects may be enrolled (e.g., in case the mean maximum observed human exposure value at the highest dose is at least 50% lower than the AUC at the NOAEL in rat [22,625 ng.h/mL]). In each cohort, 9 subjects will be randomised to receive multiple doses of MT-6345 and 3 subjects will be randomised to receive matching doses of placebo. The current dosing regimen in Part 3 is anticipated to be 14 days multiple-dose administration of MT-6345 or placebo capsules once daily on Days 1 to 14. The duration of dosing may be altered based upon emerging PK data but will not exceed 28 days.
 
The MAD cohorts may consist of sentinel dosing (1 subject will receive MT-6345 and 1 subject will receive matched placebo). Whether sentinel cohorts are needed will be decided based upon review of prior SAD and MAD cohorts. The remaining 10 subjects, of whom 8 subjects will receive MT-6345 and 2 subjects will receive placebo, will be dosed when the first MT-6345 dosed sentinel subject is predicted to have reached steady state concentration of MT-6345 (five half-lives).
 
The dose levels are planned to be administered in ascending order. Progression to the next dose level, and dose selection, will be based on the safety, tolerability and available PK data from Part 1 and the preceding dose cohort in Part 3 (safety and tolerability data up to 72 hours after the last dose and available PK data up to 24 hours after the last dose, from a minimum of 10 subjects [MT-6345 n≥7] in the preceding dose cohort).
 
The anticipated doses are [REDACTED] and [REDACTED] once daily; however, the choice of doses will be reviewed and may be altered based on the emerging data.
 
Part 4: Gender effect
 
One cohort of eight healthy Caucasian females, aged 18 to 55 years, who meet the study eligibility criteria, will be investigated to determine the effect of gender on PK following a single oral dose of MT-6345. The anticipated dose is [REDACTED] however, this may be modified based on emerging PK, safety and tolerability data from Part 1. The dose selected will not be confirmed nor administered until safety, tolerability and PK data from the intended dose level in Part 1 has been reviewed and deemed acceptable. Subjects will be randomised (MT-6345, n=6: placebo, n=2) to receive a single dose of MT-6345 or placebo in a fasted state (for at least 10 hours).
 
Part 5: Race effect – Japanese
 
One cohort of eight healthy Japanese males, aged 18 to 55 years, who meet the study eligibility criteria, will be investigated to determine the effect of race on PK following a single oral dose of MT-6345. The anticipated dose is [REDACTED] however, this may be modified based on emerging PK, safety and tolerability data from Part 1. The dose selected will not be confirmed nor administered until safety, tolerability and PK data from the intended dose level in Part 1 has been reviewed

--	---

Europe/Mitsubishi Tanabe Pharma Europe Ltd

STUDY PROTOCOL

	
and deemed acceptable. Subjects will be randomised (MT-6345, n=6: placebo, n=2) to receive a single dose of MT-6345 or placebo in a fasted state (for at least 10 hours).
 
The same dose will be used for each cohort in Parts 2, 4 and 5.

Planned number of subjects:	
Up to 100 subjects are planned to be enrolled, which may be extended to 120 subjects if additional cohorts are included in Parts 1 and 3 of the study:
 
Part 1: 48 healthy male Caucasian subjects allocated to one of six dose cohorts comprising 8 subjects each. One additional cohort of 8 subjects may be enrolled.
 
Part 2: 8 healthy male Caucasian subjects (cohort selected from Part 1).
 
Part 3: 36 healthy male Caucasian subjects allocated to one of three dose cohorts comprising 12 subjects each. An additional cohort of 12 subjects may be enrolled.
 
Part 4: 8 healthy female Caucasian subjects.
 
Part 5: 8 healthy Japanese male subjects.

Subject population:	
Parts 1, 2 and 3: healthy male Caucasian subjects aged 18 to 55 years.
 
Part 4: healthy female Caucasian subjects aged 18 to 55 years.
 
Part 5: healthy male Japanese subjects aged 18 to 55 years.

Main inclusion criteria:	
 
1. Able to provide written informed consent to participate in this study after reading the participant information sheet and Informed Consent Form, and after having the opportunity to discuss the study with the Investigator or designee.
 
2. Healthy and free from clinically significant illness or disease as determined by medical history, physical examination, laboratory and other tests at Screening and Day -1.
 
3. [REDACTED]
 
4. [REDACTED]
 
5. A body weight of <math>\geq 60</math> kg for males and <math>\geq 50</math> kg for females and a body mass index (Quetelet index) ranging from 18 to 30.0 <math>\text{kg}/\text{m}^2</math> inclusive at Screening and Day -1.
 
6. [REDACTED]
 
7. [REDACTED]
 
8. In the Investigator's opinion, subject is able to understand the nature of the study and any risks involved in participation, and willing to cooperate and comply with the Protocol restrictions and requirements.
 
9. [REDACTED]
 

Main exclusion criteria:	
 
1. Subjects with clinically significant (in the opinion of the Investigator) endocrine, thyroid, hepatic, respiratory,
 

Europe/Mitsubishi Tanabe Pharma Europe Ltd

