## 1.5 Clinical studies

No clinical studies have been conducted to date; MT-6345-E01 is a first-in-man study.

Europe/Mitsubishi Tanabe Pharma Europe Ltd  
STUDY PROTOCOL

---

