**Part 1: Single ascending dose (SAD)**

Up to 48 healthy Caucasian males, aged 18 to 55 years who meet the study criteria will be allocated to six cohorts of 8 subjects each. One additional cohort of 8 male subjects may be enrolled (e.g., in case the mean maximum observed human exposure value at the highest dose is at least 50% lower [i.e., 22,625 ng.h/mL] than the AUC at the NOAEL in rat [45,250 ng.h/mL]). In each cohort, 6 subjects will be randomised to receive a single dose of MT-6345 and 2 subjects will be randomised to receive a matching dose of placebo.

All cohorts will have 2 sentinel subjects of whom 1 subject will receive MT-6345 and 1 subject will receive matched placebo. The remaining 6 subjects, of whom 5 subjects will receive MT-6345 and 1 subject will receive placebo, will be dosed at least 24 hours following the sentinel subjects.

The dose levels are planned to be administered in ascending order. Subjects will receive a single dose of MT-6345 or placebo in a fasted state (for at least 10 hours). Progression to the next dose level, and dose selection, will be based on all available safety and tolerability data up to at least 48 hours post-dose and available PK data (up to at least 24 hours post-dose) from a minimum of 6 subjects (MT-6345 n≥4) in the preceding dose cohort.

The dose administered to Cohort 1 will be [REDACTED]. The anticipated dosing schedule is [REDACTED], [REDACTED] and [REDACTED]. The maximum dose in Part 1 (SAD) is anticipated to be [REDACTED] however, this will be selected based upon emerging PK, safety and tolerability data from previous cohorts, but will not exceed an individual exposure limit of 45,250 ng.h/mL (AUC0-24h).

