**Part 2: Food effect**

A single cohort from Part 1 (anticipated to be Cohort 3; [REDACTED] MT-6345) will be selected to return for a second treatment period to investigate the effect of food (after a Food & Drug Administration [FDA]-approved high-fat breakfast) on the PK of MT-6345. There will be a minimum of 15 days

Europe/Mitsubishi Tanabe Pharma Europe Ltd  
STUDY PROTOCOL

between the last dose administration in Part 1 and the first dose administration in Part 2. Subjects in Part 2 will receive the same dose (active or placebo) that they received in Part 1.

The dose and cohort selected for Part 2 will not be confirmed until safety, tolerability and PK data from the intended dose level in Part 1 has been reviewed and deemed acceptable. The intention is for all 8 subjects to be dosed sequentially on the same day.

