## Appendix 1 Pharmacokinetic Parameter Calculations

Actual blood sampling times will be used in the calculation of pharmacokinetic parameters

All concentrations below the LLOQ will be set at zero for pharmacokinetic calculations

When Kel is missing (or cannot be determined),  $t_{1/2}$ ,  $AUC_{0-\infty}$ ,  $AUC\%_{ex}$ , CL/F, MRT, Vz/F and Vss/F will not be calculated.

PK Parameter Calculations		
Parameters	Unit	Calculation
$C_{max}$	ng/mL	will be determined by visual inspection
$AUC_{0-\infty}$	ng·h/m L	$AUC_{0-\infty} = AUC_{0-last} + AUC\%_{ex}$
$AUC\%_{ex}$	ng·h/m L	$AUC_{exp} = C_{last} / Kel$ $C_{last}$ : last measurable concentration
$AUC_{0-last}$	ng·h/m L	will be calculated using the linear trapezoidal method and actual times $AUC_{0-la} = \sum_{i=1}^n \frac{t_i - t_{i+1}}{2} (C_{i-1} + C_i)$
$t_{max}$	h	Measured time of $C_{max}$
$t_{1/2}$	h	$t_{1/2}$ will be determined as: $t_{1/2} = \log_e (2) / Kel$
Kel	/h	
The exponential rate constant of the terminal phase, Kel, will be estimated by log-linear regression, if determinable. The number of data points included in the regression will be determined by visual inspection. Wherever possible, a minimum of 3 data points will be used in the estimation of Kel.
 
During the analysis, this calculation method repeats regressions using the last three points with non-zero concentrations, then the last four points, last five, etc. The time of maximum concentration (tmax) will be excluded from the estimation of Kel.
 
Points with a value of zero for the dependent variable are excluded.
 
For each regression, an adjusted <math>R^2</math> is computed
 $Adjusted R^2 = 1 - \frac{(1 - R^2) \times (n - 1)}{(n - 2)}$

		
where n is the number of data points in the regression and <math>R^2</math> is the square of the correlation coefficient.
 
The regression with the largest adjusted <math>R^2</math> is selected to estimate <math>K_{el}</math>, with these caveats:
 
 
- If the adjusted <math>R^2</math> does not improve, but is within 0.0001 of the largest adjusted <math>R^2</math> value, the regression with the larger number of points is used.
 
- <math>K_{el}</math> must be positive, and calculated from at least three data points.
 

CL/F	L/h	$CL/F = Dose / AUC_{0-\infty}$
MRT	/h	$MRT = AUMC_{0-\infty} / AUC_{0-\infty}$ AUMC 0-∞ : area under the first moment curve extrapolated to infinity

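### The Part 2 PK rules make no adjustment for a quantifiable pre-dose concentration, so any drug left from the fasted dose would be counted as fed exposure

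*Protocol*

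**What the plan says.** **Design.** One Part 1 cohort "will be selected to return for a second treatment period to investigate the effect of food" (protocol 3.1, Part 2). Its reference condition is Part 1, where "Subjects will receive a single dose of MT-6345 or placebo in a fasted state (for at least 10 hours". The dose does not change: "Subjects in Part 2 will receive the same dose (active or placebo) that they received in Part 1". The order is therefore fasted then fed for everyone. The interval is stated only as a minimum: "There will be a minimum of 15 days between the last dose administration in Part 1 and first dose administration in Part 2".

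**Half-life.** Protocol 1.5 says "No clinical studies have been conducted to date; MT-6345-E01 is a first-in-man study". The visible text gives no half-life, predicted or observed.

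**Sampling.** Protocol 6.4 schedules a pre-dose sample in every single-dose part and follows each profile to 336 h. Protocol 5.2.4.1 excuses the food cohort from the Part 1 Day 15 visit. Its fasted profile therefore ends at 192 h, while its fed profile runs to 336 h.

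**Derivation.** SAP 7.1.3.2 sets BLQ values to zero and uses linear trapezoids. Appendix 1 reads Cmax by inspection, extrapolates with Clast/Kel, and states "Actual blood sampling times will be used in the calculation of pharmacokinetic parameters". The PK analysis set (SAP section 5) excludes for emesis, non-completion or non-evaluable parameters. None of these rules subtracts, flags or excludes for a quantifiable pre-dose value. SAP 8.2.1 does say which part an adverse event in the washout belongs to; there is no matching rule for drug still present after the washout.

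**Analysis.** SAP 8.3.2 summarises plasma PK parameters by dose group and fed state. SAP section 10 lists the protocol's linear mixed model among the analyses not done, and SAP section 1 gives the SAP precedence over the protocol.

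**The concern.** With a single fixed order, residual drug cannot be balanced between the two conditions: all of it falls in the fed period. Under the written rules, a quantifiable pre-dose concentration and its subsequent decline are added to fed Cmax and fed AUC. The reader of the fed-state summaries then cannot tell leftover fasted dose from a food effect.

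The Part 1 versus Part 2 contrast is the trial's only evidence on its food objective. It is also thin: SAP 3.3.2 reports that 6 subjects returned, active and placebo together. The pre-dose sample that would reveal the problem is already scheduled, but no rule uses it.

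**Working it through.** **1. Inputs from the documents.** Gap of at least 15 days = 15 x 24 = 360 h. Same dose in both periods. Last fasted sample in this cohort 192 h, last fed sample 336 h. Linear trapezoid plus Clast/Kel. The 15 days cannot be reproduced, because no half-life or washout formula is visible.

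**2. Assumptions.** Linear PK, one compartment, absorption rate 1/h, no true food effect, all samples quantifiable, gap exactly at the minimum. Half-life h is unknown and is varied.

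**3. Formula.** At the Part 2 dose the share of the Part 1 AUC still to come is 2^(-360/h). It is added to the fed AUC, so fed/fasted AUC0-inf = 1 + 2^(-360/h) when the true ratio is 1. For example, at 96 h: 360/96 = 3.75 and 2^(-3.75) = 7.43%. Cmax, pre-dose/Cmax and AUC0-last come from the same model on the protocol's sampling times.

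| Assumed h (h) | 360/h | AUC0-inf inflation | Cmax ratio | Part 2 pre-dose/Cmax | AUC0-last to 336 h over 192 h, no residual drug |
|---|---|---|---|---|---|
| 24 | 15.00 | 0.003% | 1.000 | 0.00% | 1.008 |
| 48 | 7.50 | 0.55% | 1.006 | 0.59% | 1.077 |
| 67.2 | 5.36 | 2.44% | 1.025 | 2.53% | 1.146 |
| 72 | 5.00 | 3.13% | 1.031 | 3.20% | 1.162 |
| 96 | 3.75 | 7.43% | 1.075 | 7.22% | 1.235 |
| 120 | 3.00 | 12.5% | 1.126 | 11.51% | 1.295 |

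With both periods on the same sampling grid, the trapezoidal AUC0-inf ratio agrees with the formula: 1.006 at 48 h, 1.025 at 67.2 h, 1.075 at 96 h and 1.126 at 120 h. Inflation reaches 1% at a half-life of 54 h, 5% at 83 h and 10% at 108 h. A gap longer than 15 days lowers the residual-drug figures.

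**4. Does subtraction remove it?** The measured Part 2 concentration is C_fed(t) + C(pre-dose) x exp(-Kel x t). Subtracting the second term leaves C_fed(t). Both terms share the same terminal slope, so Kel estimated from the unadjusted Part 2 profile is not distorted by the residual drug.

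**5. A separate distortion of AUC0-last.** The last column involves no residual drug at all. It arises because the fed profile can run 144 h longer than the fasted one (336 - 192). At each half-life shown it is larger than the residual-drug effect, and pre-dose subtraction does not remove it.

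**6. The opposite direction.** Protocol 4.8.5 names possible enzyme induction by MT-6345. If clearance were 10% higher in Part 2 (assumed), the net AUC ratio at h = 72 h would be 1.03125/1.10 = 0.94, and at h = 24 h about 1/1.10 = 0.91.

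**The case against.** **The effect may be negligible.** This stands. The background and dose-rationale sections are largely redacted and could hold a predicted half-life that justifies 15 days. The plan also derives a Day 1 AUC0-inf in Part 3, where sampling stops at the next dose. At 67.2 h the first 24 h would capture only 1 - 2^(-24/67.2) = 22% of the AUC, so that plan suits a shorter half-life. Against this, single-dose sampling runs to 336 h, and protocol 10.3.5.8 anticipates that the Day 1 AUC0-inf may not be calculable precisely. The documents settle neither case.

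**Safeguards exist.** Fifteen days is a minimum, and Part 1 PK at the intended dose is reviewed before Part 2 is confirmed. But that review has no residual-drug criterion, and protocol 3.4 specifies PK only to 24 h. SAP 7.4 defers PK data handling to a separate document, which could contain a pre-dose rule. The visible text there concerns invalid or erroneous data, and a true residual concentration is neither.

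**Stronger readings that the documents do not support.**
- A reader might infer that carry-over can only inflate the food effect. That holds for residual drug, not for all carry-over: induction persisting from Part 1 would lower fed exposure.
- A reader might join "The duration of dosing may be altered based upon emerging PK data but will not exceed 28 days" to "predicted to have reached steady state concentration of MT-6345 (five half-lives" and conclude that the plan contemplates half-lives up to 28 x 24/5 = 134 h, with 15.6% inflation. The five-half-lives wording governs only the staggering of optional Part 3 sentinel subjects; no passage sets the Part 3 duration by it.
- A reader might infer that a formal fed/fasted ratio and 90% CI are biased. The governing SAP no longer plans them.
- A reader might see a conflict between the 15-day gap and the adaptable Part 3 duration. The two passages do not contradict each other, and Part 2 is complete.

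**Conclusion.** The point holds as a conditional gap in the derivation rules. If any Part 2 pre-dose concentration is quantifiable, the visible SAP rules count that drug as fed exposure, and this component acts only upwards. At the 15-day minimum the AUC0-inf inflation is under 1% up to a half-life of about 48 h, about 2.5% at 67 h, 7% at 96 h and 12.5% at 120 h; Cmax behaves almost identically. These sizes rest on assumed half-lives and linear PK. They do not show that carry-over occurred.

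What is affected is a set of descriptive summaries by fed state from a small cohort. The net direction of all period effects together is unknown, because order and food are fully confounded. The unequal fasted and fed sampling also inflates fed/fasted AUC0-last when late samples are quantifiable, with or without residual drug.

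**What to change.** In SAP 7.1.3.2 and Appendix 1, for Part 2 only:

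- If any pre-dose concentration is quantifiable, also derive Cmax and the AUCs after subtracting C(pre-dose) x exp(-Kel x t) from each Part 2 concentration. Use the subject's Part 2 Kel, or the Part 1 Kel if that is not estimable. Flag the subject if neither is available.
- Present adjusted and unadjusted fed-state summaries side by side.
- List each subject's actual interval between doses and the pre-dose concentration as a percentage of Cmax.
- Compare AUC over a common 0-192 h interval, since AUC0-last does not cover the same time span in the two periods.
- Describe the fed/fasted comparison as descriptive and confounded with period.

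The cost is SAP wording and a short derivation; the sample is already in the schedule. If all pre-dose values are BLQ, adjusted and unadjusted values are the same. The downside is that the adjustment assumes residual drug declines at the estimated Kel, which is least certain when the half-life is long relative to the sampling. Keeping the unadjusted results alongside makes that dependence visible.
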